3.3 Secondary Study Endpoints

- 1. Proportion of patients reaching renal endpoint (doubling creatinine/ESRF)
- 2. Mortality rates at each time point.
- 3. Length of hospital stay.
- 4. Estimated glomerular filtration rate (eGFR), serum creatinine and urine protein:creatinine ratio at each time point.
- 5. Comparison of causes of death between AKI group and controls
- 6. Comparison of levels of biomarkers of tubular injury (a panel to include NGAL and IL-18) and markers of inflammation (IL-6, hs-CRP) in those with and without progression of CKD.

4 Methods

The methods are the same as for the pilot study; the only change is that we propose to collect an additional blood sample for storage and subsequent analysis at each time point.

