4.1 Subject Selection and Withdrawal

4.1.1 Inclusion Criteria

- Age ≥18 years and ≤85yrs
- In-patient serum creatinine measurement detected by iCM electronic AKI reporting system

Exclusion Criteria

- Inability/refusal to give informed consent to participate.
- Language barrier that prevents informed postal consent.
- Death during the same hospital admission that AKI occurred.
- Receiving palliative care

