4.2.1 Group A – main study

All patients with AKI will be screened for inclusion into the study, as well as those patients tested for possible AKI but who did not sustain it. Patients will not be approached until at least two months after they have recovered from their acute illness, by which time the majority of patients will have returned home.

Recruitment, matching and consent

Patients who meet the inclusion criteria will be contacted via post and invited to participate. The control group will be matched to AKI patients on a 1:1 basis in terms of baseline eGFR (within the same CKD stage but as closely as possible) and age \pm 5yrs. In addition they will be recruited from a similar inpatient setting. Due to the proposed three year follow up, patients over 85yrs will be excluded as the reduced life expectancy due to age alone in these patients may affect the outcome measures of mortality.

Potential subjects will receive a letter of invitation along with a comprehensive patient information sheet. Interested patients will be asked to telephone a number at the Royal Derby Hospital during which patient identity will be affirmed using standard data protection questions. After confirmation that the patients are in possession of the information required to provide valid consent, they will be sent a consent form that they will sign and return in a pre-paid envelope, retaining a copy for themselves (see section 4.2.2 for more details of the consent process). If patients do not wish to participate they will be asked to confirm this by telephoning the same number. This methodology has been piloted and has been shown to be very successful in more than 300 patients to date, with very positive feedback from participants.

Each patient will be assigned a unique study number that will be used to identify all data collected for the study. This will be allocated upon recruitment. A key of patient identity and study numbers will be kept on a password-protected Trust server in a password-protected file. Any information passed onto the Medical Research Information Service will be in encrypted form. A recruitment log will be maintained and the patients' GPs will be informed of their participation in the study by letter.

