4.2.3 Group B – patients with liver disease

Recruitment, matching and consent

Many patients with cirrhosis in the UK are alcoholics and intravenous drug users. They tend to live a chaotic lifestyle with fluid residential addresses and limited access to telephone facilities. We therefore propose an alternative recruitment method to include this important patient group and facilitate participation. Patients will still be identified via the electronic AKI system but those who had their inpatient care delivered by the gastroenterology team will be screened for cirrhosis (using established definitions). Patients will not be approached until they have recovered from their acute illness.

Patients with cirrhosis and who meet the inclusion criteria will be approached on the ward prior to discharge and invited to participate by one of the research team. The control group will be matched to AKI patients on a 1:1 basis in terms of baseline eGFR (within the same CKD stage but as closely as possible) and age ± 5yrs. In addition they will be recruited from a similar inpatient setting. Due to the proposed three year follow up, patients over 85yrs will be excluded as the reduced life expectancy due to age alone in these patients may affect the outcome measures of mortality.

Potential subjects will receive a letter of invitation along with a comprehensive patient information sheet which they can read for 24 hours. After addressing any concerns or queries, interested patients will be asked to sign a consent form that they will sign and return to a member of the research team prior to discharge, retaining a copy for themselves. If patients do not wish to participate they will be asked to confirm this and will continue to receive standard of care.

Each patient will be assigned a unique study number that will be used to identify all data collected for the study. This will be allocated upon recruitment. A key of patient identity and study numbers will be kept on a password-protected Trust server in a password-protected file. Any information passed onto the Medical Research Information Service will be in encrypted form. A recruitment log will be maintained and the patients' GPs will be informed of their participation in the study by letter.

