4.4 Prior and Concomitant Therapy

Details of the hospital admission during which the patients were initially identified (either with AKI or screened as NAKI) will be collected from coding data on the hospital's PAS system. This will include primary diagnosis, secondary diagnoses and co-morbidity (specifically diabetes, hypertension, cardiovascular disease, active malignancy and for the liver subgroup aetiology and severity of liver disease). The patient's highest AKI stage, length of hospital stay, and discharge creatinine will be recorded. Acute dialysis treatments and dialysis independence will be determined for those patients who require acute RRT during the course of AKI.

5 Laboratory Assays

Renal function (urea and electrolytes) will be obtained at recruitment (this will be 3mnths after the episode of AKI/NAKI). Then at 1 year, 3 years, 5 years and 10 years after AKI/NAKI (approximately 9mnths, 33mnths, 57 mnths and 117 mnths post recruitment). These samples form part of routine clinical care for patients recovering after an episode of AKI or with CKD and would normally be performed by the General Practitioner. Participants will be asked not to eat meat for 12 hours prior to the blood tests (to avoid a potential effect on the creatinine assay) and will be able to have the samples taken at GP surgeries, community hospitals (including London Road) or RDH. Results will be available via the hospital results system.

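### Total index-admission stay is listed as a secondary endpoint, yet for AKI that begins after admission it counts pre-AKI days, so a group comparison can show longer stay with no AKI effect

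*Protocol*

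**What the plan says.** Section 3.3, item 3, reads in full "Length of hospital stay". It gives no start point and no method of comparison. Section 2 says that the study pursues its objectives by comparing outcomes in hospitalised patients with and without AKI.

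Section 4.4 shows which stay is meant and how it is held: "Details of the hospital admission during which the patients were initially identified (either with AKI or screened as NAKI) will be collected", and "The patient's highest AKI stage, length of hospital stay, and discharge creatinine will be recorded". This is one value per patient, with no division at AKI onset.

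Four other provisions bear on it:

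- **Cases.** Section 3.1 takes in AKI episodes from any inpatient location and does not restrict to AKI present on admission.
- **Controls.** Sections 4.2.1 and 4.2.3 match 1:1 on baseline eGFR and age and recruit from a similar setting. Time already spent in hospital is not a matching factor. A control is a patient tested who did not develop AKI.
- **Survivors.** The exclusion criteria in section 4.1 include "Death during the same hospital admission that AKI occurred" and inability or refusal to consent.
- **Time of approach.** Group A is approached "at least two months after they have recovered from their acute illness, by which time the majority of patients will have returned home". Group B "will be approached on the ward prior to discharge and invited to participate by one of the research team".

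**The concern.** Group membership depends on what happens during the interval being measured. A patient with hospital-acquired AKI must first have stayed in hospital long enough to develop it, and a longer stay gives more opportunity to be flagged. A control is, by definition, someone whose stay ended without AKI. Comparing total stay therefore credits pre-AKI days to AKI. This is immortal-time bias, and matching on eGFR, age and setting does not remove it.

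At stake is one secondary endpoint: a largely structural difference could be read as a consequence of AKI. The primary endpoints, death and CKD progression, are not touched.

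**Working it through.** The protocol gives no figure for stay, so there is none to reproduce. It also gives no discharge rate, in-hospital AKI rate, in-hospital death rate or hospital-acquired share. **All rates below are assumptions.**

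**Notation.** Daily discharge rate d, unchanged by AKI (the no-effect case); in-hospital AKI rate h; share of AKI that is hospital-acquired p. Rates are constant over the stay.

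**Step 1: no in-hospital death.**

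- Control mean stay: 1/(d+h)
- Hospital-acquired AKI: 1/(d+h) + 1/d
- AKI present on admission: 1/d
- Spurious excess, AKI minus control: 1/d − (1−p)/(d+h)

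| Mean stay 1/d (days) | h per day | Hospital-acquired AKI vs control (days) | Excess, p = 0.3 | p = 0.5 | p = 0.7 |
|---|---|---|---|---|---|
| 5 | 0.02 | 9.5 vs 4.5 | 1.8 | 2.7 | 3.6 |
| 5 | 0.04 | 9.2 vs 4.2 | 2.1 | 2.9 | 3.8 |
| 8 | 0.02 | 14.9 vs 6.9 | 3.2 | 4.6 | 5.9 |
| 8 | 0.04 | 14.1 vs 6.1 | 3.8 | 5.0 | 6.2 |

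First row, p = 0.3: 5 − 0.7 × 4.545 = 1.8 days. Last row, p = 0.7: 8 − 0.3 × 6.061 = 6.2 days. Simulation of 400,000 admissions per scenario agrees.

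**Step 2: in-hospital death added, survivors only.** With death rate m before AKI and m2 after it, the excess is 1/(d+m2) − (1−p)/(d+m+h). The ranges are d 0.10 to 0.20, h 0.005 to 0.02, m 0.005, and m2 either 0.005 or 0.03 per day.

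- All AKI hospital-acquired (p = 1): +4.3 to +9.5 days
- p = 0.5: about +2.0 to +5.5 days
- p = 0.3: about +1.0 to +3.9 days
- All present on admission (p = 0): +0.1 to +1.5 days if AKI does not raise in-hospital death (m2 = 0.005); −0.1 to −1.4 days if it does (m2 = 0.03)

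The sign reverses when 1−p exceeds (d+m+h)/(d+m2). With d = 0.10, m = 0.005, h = 0.01 and m2 = 0.03 this is 0.115/0.13 = 0.88, so more than 88% of AKI would have to be present on admission.

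**Step 3: shape of the stay distribution.** Gamma stays with mean 7 days, h = 0.01 and all AKI hospital-acquired give 16.2 vs 6.4, 13.5 vs 6.5 and 10.3 vs 6.8 days for shapes 0.7, 1 and 2. The direction is the same.

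**Step 4: does counting from the alert remove the bias?** That depends on the comparator.

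- *Never-AKI controls, as the protocol defines them, counted from the same hospital day.* Remaining stay is 1/d for AKI and 1/(d+h) for controls. In the four scenarios of step 1 this is 5.0 vs 4.5, 5.0 vs 4.2, 8.0 vs 6.9 and 8.0 vs 6.1 days, so about 0.5 to 1.9 days remain.
- *Patients AKI-free and in hospital on that day, whatever happens later.* With constant rates both sides have mean 1/d and the expected gap is zero. In the gamma simulations (3,000 AKI cases) the remaining stays were 8.75 vs 8.00, 7.01 vs 7.33 and 5.35 vs 5.30 days. The residual is −0.3 to +0.75 days, against 3.6 to 9.9 days for total stay.

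**The case against.** The strongest reply is that the protocol never states the comparison at issue. Items 5 and 6 of section 3.3 use the word comparison; item 3 does not. Section 8.2 specifies no AKI-versus-control test of stay and mentions secondary outcomes only as terms explored for CKD progression and 12-month mortality. A start point could be set in an analysis plan that is not shown. This limits the point: no biased test is written down. It does not dispose of it, because section 2 frames the study as a comparison of outcomes, a listed endpoint falls naturally under that, and the protocol collects only total stay and gives controls no index day.

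A reader might infer more than the documents support:

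- **That the bias is upward by construction.** It is upward for AKI arising in hospital. The share of such AKI is not given, and step 2 shows that the sign can reverse.
- **That completion before recruitment is itself a bias.** Stay is read from hospital records, so the time of approach does not distort it. Section 4.2.1 says only that most of Group A are home by then, and Group B is approached before discharge.
- **That restriction to consenting survivors inflates the AKI stay.** It limits whom the result describes but has no fixed direction, and can shorten apparent stay after AKI.
- **That the result would be presented as a resource consequence of AKI.** The protocol plans no such report. Section 1.1 describes longer stay as an association and leaves causality open.

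The magnitude rests wholly on assumed rates and ignores matching on setting, which might absorb part of the difference. That also stands.

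**Conclusion.** The point holds in a limited form. As recorded, total index stay cannot separate days before AKI from days after it, and the control definition and matching do not correct for this. A group comparison can therefore show a longer stay after AKI when AKI has no effect. The excess is about 2 to 6 days if 30 to 70% of AKI is hospital-acquired, with mean stays of 5 to 8 days and an in-hospital AKI rate of 2 to 4% per day, all assumed. It shrinks, and may reverse, as the share present on admission approaches one and AKI raises in-hospital death. One secondary endpoint outside the stated objectives is affected. The change is worth making because it costs almost nothing.

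**What to change.** Move item 3 out of the secondary endpoints in section 3.3 and report stay with the admission characteristics that section 4.4 already collects. State that it describes consenting survivors of the admission and that a group difference is not to be interpreted as an effect of AKI.

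If a comparison is wanted, count days from the AKI alert to discharge. Compare with patients still in hospital and AKI-free on the same hospital day, including those who develop AKI later. Using the study's never-AKI controls from a same-day start would reduce the bias but not remove it.

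The first option costs one line and one secondary endpoint. The second needs alert dates and an index day for each comparator. These should be obtainable from the electronic reporting system, although the protocol does not say that they will be extracted. It also needs a comparator set that differs from the study's matched controls.

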4.1 Subject Selection and Withdrawal

4.1.1 Inclusion Criteria

- Age ≥18 years and ≤85yrs
- In-patient serum creatinine measurement detected by iCM electronic AKI reporting system

Exclusion Criteria

- Inability/refusal to give informed consent to participate.
- Language barrier that prevents informed postal consent.
- Death during the same hospital admission that AKI occurred.
- Receiving palliative care

4.2 Subject Recruitment and Screening

There will be two methods of patient recruitment. For the majority of patients, the recruitment will occur as in the pilot study and is detailed in section 4.2.1. For a specific group of patients with liver disease, we propose a modified method of recruitment to adapt to the challenges of participant engagement in this particular patient group; this is detailed in section 4.2.3.

All patients will be identified via the AKI electronic reporting system. This system will electronically identify all patients that have sustained AKI or been screened for possible AKI but who did not sustain it. This database is currently used internally to monitor trends and assess effectiveness of clinical care. We will apply for specific ethical approval from the National Information Governance Board (approval for the same methodology already in place for the pilot study) to allow the identification of potential participants from this database, even though their inpatient care may have been delivered by another clinical team.

4.2.1 Group A – main study

All patients with AKI will be screened for inclusion into the study, as well as those patients tested for possible AKI but who did not sustain it. Patients will not be approached until at least two months after they have recovered from their acute illness, by which time the majority of patients will have returned home.

Recruitment, matching and consent

Patients who meet the inclusion criteria will be contacted via post and invited to participate. The control group will be matched to AKI patients on a 1:1 basis in terms of baseline eGFR (within the same CKD stage but as closely as possible) and age \pm 5yrs. In addition they will be recruited from a similar inpatient setting. Due to the proposed three year follow up, patients over 85yrs will be excluded as the reduced life expectancy due to age alone in these patients may affect the outcome measures of mortality.

Potential subjects will receive a letter of invitation along with a comprehensive patient information sheet. Interested patients will be asked to telephone a number at the Royal Derby Hospital during which patient identity will be affirmed using standard data protection questions. After confirmation that the patients are in possession of the information required to provide valid consent, they will be sent a consent form that they will sign and return in a pre-paid envelope, retaining a copy for themselves (see section 4.2.2 for more details of the consent process). If patients do not wish to participate they will be asked to confirm this by telephoning the same number. This methodology has been piloted and has been shown to be very successful in more than 300 patients to date, with very positive feedback from participants.

Each patient will be assigned a unique study number that will be used to identify all data collected for the study. This will be allocated upon recruitment. A key of patient identity and study numbers will be kept on a password-protected Trust server in a password-protected file. Any information passed onto the Medical Research Information Service will be in encrypted form. A recruitment log will be maintained and the patients' GPs will be informed of their participation in the study by letter.

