3.1 General Design

This is a long-term longitudinal observational case-control study. Basic blood tests to include measuring renal function, haemoglobin, albumin and proteinuria will be measured at study entry as well as 1 year, 3 years, 5 years and 10 years after AKI (approximately 9months, 33months, 57 months and 117 months after recruitment). Samples will also be collected and stored at each of these time points for subsequent biomarker measurement; these will consist of inflammatory markers (IL-6, high sensitivity CRP) and plus a panel of biomarkers of tubular injury (to include NGAL and IL-18). Included patients will have baseline demographics, co-morbidity and acute illness details extracted from the hospital PAS system. AKI stage and baseline renal function (that prior to sustaining AKI) will be extracted from the electronic AKI reporting system currently in clinical use at the Royal Derby Hospital. This novel system identifies all episodes of AKI from every inpatient location and also reports severity as per AKIN staging; the diagnostic accuracy of this system has been confirmed and reported previously [16].

Patients receiving acute dialysis during the episode of AKI will be identified from renal unit and intensive care unit databases; the renal database (Vitaldata) will be used to identify those patients who subsequently require chronic renal replacement therapy (RRT). The Medical Research Information

Service (MRIS, an arm of the NHS Information Centre) will be used to accurately track survival data of participants to **ten** years after the AKI episode.

A pilot study, specifically designed to test this methodology and recruitment process is currently underway, and demonstrates that the proposed recruitment, consent and matching processes are both practicable and feasible (recruitment rate ~20%, with approximately 15 participants recruited per week).

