8.2 Statistical Methods

Statistical analysis will be performed using SPSS v19.0 and Stata v11. Descriptive statistics will be used to summarise baseline variables in AKI and control groups. Univariate parametric or non-parametric analysis will be done to compare the two groups at baseline. Kaplan-Meier curves will be constructed to compare the primary endpoints, renal end-point and mortality between the two groups using the Log-Rank test. A Cox proportional hazard model will be used to test the effect of AKI on primary endpoints adjusted for age, gender, (race if possible), co-morbidity (diabetes, hypertension, malignancy, cardiovascular disease), baseline renal function, proteinuria, requirement for acute dialysis and multiple episodes of AKI. Conditional logistic regression will be performed for exploring the effect of AKI matched patients and secondary outcomes on the proportion of patients with CKD progression and on their mortality status at 12 months. Participants with cirrhosis will be included in the main analysis, but their co-morbid conditions will be accounted for in the statistical analysis.

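### The mortality Cox model leaves out the admission diagnosis that the study collects, and control selection refers to the acute illness only through an undefined similar setting, so some confounding by the admitting illness remains

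*Protocol*

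**What the plan says.** **Control selection.** Section 4.2.1 has controls "matched to AKI patients on a 1:1 basis in terms of baseline eGFR (within the same CKD stage but as closely as possible"), and to within five years of age. It then adds: "In addition they will be recruited from a similar inpatient setting". Section 4.2.3 uses the same rule for patients with cirrhosis. Neither section says whether setting means ward, specialty, urgency of admission or diagnosis.

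**Data collected.** Section 3.1 states: "Included patients will have baseline demographics, co-morbidity and acute illness details extracted from the hospital PAS system". Section 4.4, on coding data for the index admission, states: "This will include primary diagnosis, secondary diagnoses and co-morbidity".

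**Analysis.** Section 8.2 uses a Cox model "to test the effect of AKI on primary endpoints adjusted for age, gender, (race if possible), co-morbidity", and the list continues with "diabetes, hypertension, malignancy, cardiovascular disease), baseline renal function, proteinuria, requirement for acute dialysis and multiple episodes of AKI". Primary diagnosis is not in the list. The conditional logistic regression in the same section names no such covariate either.

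**Purpose.** Section 2 aims at the long-term effects of AKI on CKD progression and mortality, comparing hospitalised patients of similar characteristics. Section 1.1 treats it as open whether the known associations are causal. Death is the first primary endpoint in section 3.2.

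**The concern.** The reason for admission largely precedes AKI, can bring it on, and can predict later death. It is therefore an ordinary confounder of the AKI mortality comparison. If AKI patients were admitted with more serious illness than their controls, and neither the matching nor the model takes this up, part of the excess mortality from that illness will be credited to AKI. The study wants to separate the two, and it already holds the coded diagnosis that would help.

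This goes beyond detail that a protocol may leave to a statistical analysis plan, because section 8.2 fixes an explicit covariate list and section 4.2.1 fixes the matching rule.

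**Working it through.** The protocol gives no figure on this point, so there is nothing to reproduce. The check sets the passages side by side and then illustrates the possible size.

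**1. Which design and model elements bear on the admitting illness?**

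| Element | Where | Does it balance the reason for admission? |
|---|---|---|
| Baseline eGFR/CKD stage and age | 4.2.1, 4.2.3 | No; these are chronic characteristics |
| Similar inpatient setting | 4.2.1, 4.2.3 | Possibly in part; undefined |
| Diabetes, hypertension, malignancy, cardiovascular disease | 8.2 | In part; malignancy and cardiovascular disease overlap with causes of admission |
| Baseline renal function, proteinuria | 8.2 | No |
| Acute dialysis, multiple AKI episodes | 8.2 | No; both arise from AKI |
| Exclusion of in-hospital death (AKI admission) and palliative care | 4.1.1 | In part; removes the most severe cases |
| Approach at least two months after recovery | 4.2.1 | In part; Group A only |
| Primary and secondary diagnoses | 4.4 | Would help, but not in the model |

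Section 4.4 records acute dialysis for the course of AKI, and sections 4.3 and 8.3 exclude controls who later sustain AKI. The two AKI-related covariates therefore describe essentially one group only and cannot balance admitting illness between the groups. Group B is approached on the ward before discharge (section 4.2.3), so the two-month delay does not apply there.

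**2. How large could the residual bias be?** Every input here is an assumption; the protocol gives no diagnosis distributions or hazards. Take one binary high-risk admission diagnosis with hazard ratio *h* for death, and prevalence *p1* in the AKI group and *p0* in controls. With no true AKI effect, the apparent ratio is approximately

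B = (1 + p1(h − 1)) / (1 + p0(h − 1))

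| p1 | p0 | h | B |
|---|---|---|---|
| 0.30 | 0.20 | 1.5 | 1.15 / 1.10 = 1.05 |
| 0.40 | 0.20 | 2 | 1.40 / 1.20 = 1.17 |
| 0.50 | 0.20 | 2 | 1.50 / 1.20 = 1.25 |
| 0.50 | 0.20 | 3 | 2.00 / 1.40 = 1.43 |

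The formula is a risk-ratio bias factor and only approximates bias in a hazard ratio. The prevalences should be read as the imbalance left after matching and adjustment, not as raw differences. A constant *h* is also assumed, although follow-up runs to ten years.

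**The case against.** The strongest reply is that the acute illness is not ignored. Controls are inpatients from the same reporting system who were tested for possible AKI. Deaths during the AKI admission and palliative patients are excluded, Group A is approached only after recovery, and malignancy and cardiovascular disease are in the model. Section 8.2 also says that co-morbid conditions of participants with cirrhosis will be accounted for. This stands in part: a reader might infer that the admitting illness is wholly uncontrolled, and the protocol does not support that. What remains is residual confounding. These restrictions do not equalise diagnoses among the survivors who are followed.

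Setting may have been applied strictly in practice. A reader might picture a septic AKI patient paired with an elective control on the same ward. The wording does not rule this out, but nothing shows that it happens. Section 4 carries the methods over from the pilot, and how the pilot applied the term cannot be seen.

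The direction is not certain. Only consenting survivors enter, at a pilot recruitment rate of about 20% (section 3.1). If healthier AKI survivors are more likely to join, that selection could offset the bias. An acute-illness hazard may also wane over ten years. Both points stand.

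Finally, coded primary diagnosis is not a clean baseline variable. Section 4.4 does not say when it is assigned, and it may be AKI itself. Stratifying on it without care would partly condition on the exposure. This also stands, and the fix has to deal with it.

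**Conclusion.** The point holds as one of residual confounding. Control selection ties the groups to the acute illness only through an undefined term. The explicit Cox list omits a collected variable that plausibly affects both AKI and later death. These are facts of the text.

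The consequence for the mortality hazard ratio follows in kind but not in amount. Bias away from the null is the more likely direction, but this is a judgement and cannot be derived from the protocol. The range of 1.05 to 1.43 rests wholly on assumed prevalences and hazards, and nothing shows which scenario applies. A reader might go on to infer that a modest reported hazard ratio would be fully explained by the admitting illness; the protocol gives no basis for that.

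The correction is worth making because it is cheap and bears on a primary comparison.

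**What to change.** In section 8.2, add broad primary-diagnosis group, taken from the PAS coding already collected, to the mortality Cox model. Either strata or a covariate will do. Report the AKI hazard ratio with and without it, so that readers can see how far the estimate moves.

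Three safeguards belong in the text:

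- Where AKI itself is the coded primary diagnosis, assign the group from the underlying cause in the secondary diagnoses, so that the model does not condition on the exposure.
- Add emergency versus elective admission only if the acute illness details from PAS are confirmed to hold it. Section 4.4 does not list it.
- Do not adjust for items that follow AKI, such as ICU care or length of stay, when estimating the overall effect of AKI.

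I would not ask for a new matching rule for any remaining recruitment, since that would mix two rules in one cohort. Nor is a propensity score for the renal endpoint needed to answer this point; it is one choice among acceptable methods.

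The cost is some work to group the coded diagnoses and a small loss of precision. No new data from patients are needed.
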